
Study Design

Phase*

Not applicable

Design

All subjects will receive active TMS to our novel fMRI-guided targeting method over the course of 3 days, preceded and followed by a 2hr MRI scan during which TMS is administered throughout.

Study duration

Enrollment of subjects in this study will take place over approximately 2 years. Each subject will complete 8 study visits over the course of ~3 weeks. The study schedule is as follows: Visit 1: Consenting / Screening procedures (approx. 3 hours) Visit 2: Baseline MRI Scan to determine TMS targets (1 hour) Visit 3: TMS/ fMRI Scan #1 & Assessments (approx. 3 hours) Visits 4-6: Mini TBS Visits - TMS to the fMRI-guided site (approx. 1hr each) Visit 7: Follow-Up Visit - TMS/fMRI Scan #2 (approx. 3 hours)

Resources necessary for human research protection

Describe research staff and justify that the staff are adequate in number and qualifications to conduct the research. Describe how you will ensure that all staff assisting with the research are adequately informed about the protocol and their research related duties. Please allow adequate time for the researchers to conduct and complete the research. Please confirm that there are adequate facilities for the research.

Staff will be trained on the protocol and inclusion/exclusion criteria. TMS protocols, as well as clinical and neurological assessments, will be administered by specially-trained staff in the Center for Neuromodulation in Depression and Stress the University of Pennsylvania Department of Psychiatry. All TMS staff will be trained by the PI ([name].) and the Center Director ([name].). Other facilities will include various laboratory spaces specializing in advanced computing and analysis of neuroimaging and cognitive datasets. Scans will be conducted on a Siemens Prisma 3 Tesla whole-body MRI with a 64-channel head/neck array, housed in the Center for Advanced Magnetic Resonance Imaging and Spectroscopy (CAMRIS). Additional MRI resources, such as a mock scanner, may be accessed from the Center for Functional Neuroimaging (CfN).

Characteristics of the Study Population

Target population

Patients will be diagnosed with current Major Depressive Disorder as determined by meeting the DSM criteria for MDD; a subset of patients will be diagnosed with current Persistent Depressive Disorder (PDD) instead of current MDD, as per the May 2018 protocol. They will be otherwise healthy, right-handed, adults aged 18-60 years.

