Subjects enrolled by Penn Researchers

95

Subjects enrolled by Collaborating Researchers

0

Accrual

All recruitment will be conducted through the University of Pennsylvania and surrounding community to find 40 individuals with MDD to complete the study with usable data. It is assumed that there will be approximately 55 participants who screen fail, are lost to follow up, withdraw, or complete without usable data. Therefore, we estimate that we will need to consent/enroll up to 95 participants overall, in order to adequately test the hypotheses.

Key inclusion criteria

1. 18-60, male or female, inclusive 2. Meets DSM-5 criteria for major depressive disorder (MDD) 3. Capacity to give informed consent and follow study procedures 4. Sufficient command of English language to understand and respond to written as well as verbal instructions 5. Right- handed

Key exclusion criteria

1. Significant disability (e.g., intellectual disability, blindness, deafness, etc.) that would interfere with testing procedures
2. MRI contraindications (e.g., foreign metallic implants, pacemaker, shrapnel or other metal in/on the body that cannot be removed, claustrophobia, etc.)
3. Additional TMS contraindications (e.g., seizure disorder, CNS active disorder, etc.)
4. Medication use that substantially reduces seizure threshold to TMS (olanzapine, chlorpromazine, lithium) and unwilling or unable medically to safely withdraw, at least two weeks prior to TMS, from these medications
5. Opiate medication, antihypertensive medication, or any medication that interferes with blood flow (interferes with fMRI recordings)
6. Current use of psychiatric medication, and unable/ unwilling to safely withdraw 2 weeks prior to study
7. Known neurological disorders (e.g., multiple sclerosis, encephalopathy, seizure disorder, brain tumors, etc.)
8. Diagnosis(es) of an exclusionary DSM-5 Diagnosis, including (but not limited to) bipolar disorder, schizophrenia, current severe substance use disorder, or any other diagnosis as determined by PI.
9. Refusal to abstain from illicit drug use for duration of the study
10. Refusal to abstain from alcohol within 24 hours of scans
11. Woman who is pregnant, breastfeeding, or trying to become pregnant (based on woman's attestation alone)
12. Any other factor that the investigator decides may affect patient safety or compliance (e.g., distance greater than 100 miles from procedure site)

Vulnerable Populations

Children Form

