Subjects will be compensated through University of Pennsylvania supported Greenphire ClinCard. This is a reloadable prepaid card (similar to a debit/credit card) which allows funds to be available immediately. Study staff will provide participants with a ClinCard Cardholder FAQ: US document (attached). Subjects will receive compensation at the end of their study completion. If subjects do not fully complete the study, they will receive compensation for the parts of the study they did complete, based on the following outline: Visit 1: Clinical Interview (\$20.00) Visit 2: Baseline MRI Scan to determine TMS targets (\$40.00) Visit 3: Baseline TMS/MRI Scan #1 (\$60.00) Visit 4-6: TMS to the fMRI-guided site (\$70.00 each, \$210.00 total) Visit 7: Follow-up TMS/MRI Scan #2 (\$120.00) Total compensation for full study completion is \$510.00 for each subject. Subjects who do not feel comfortable with the Greenphire ClinCard may be compensated by a check, in lieu of the ClinCard. We are not stating this option in the ICF, as we would prefer all participants to use the ClinCard for consistency; however, we acknowledge that not all individuals will feel comfortable with this method and therefore, if during the consenting process or at any time during the study, a participant expresses discomfort, we will then verbally offer them the option of being paid with a check.

Study Procedures

Suicidal Ideation and Behavior

Does this research qualify as a clinical investigation that will utilize a test article (ie- drug or biological) which may carry a potential for central nervous system (CNS) effect(s)?

No

Procedures

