Pre-screening: Participants may complete an online or phone screening form to see if they meet basic eligibility requirements. Screening will include the collection of contact information, basic demographics, and a brief medical and psychiatric history. Screenings will be recorded in REDCap; this data will be retained indefinitely. The screening data will not be used for analyses and will only be retained to help research staff monitor recruitment resources, reasons individuals do not meet eligibility, and to help avoid rescreening the same individuals. We request a waiver of HIPAA authorization for this aspect of the study. Visit 1/ Screening Visit: Informed consent will be obtained upon arrival for an initial visit and before any study-related procedures are conducted. The rest of this screening visit will include a structured diagnostic interview (SCID-5), psychiatric and medical evaluation, collection of demographic information, and a demonstration of TMS. For participants that indicated regular drug use in prescreening or screening forms, we may use a urine drug screen to confirm adherence to study policy of abstinence. The urine drug screen will be collected by study staff; test results will be stored in REDCap and the test destroyed after. The information collected in this initial visit will determine if the subject meets all inclusion criteria. Upon meeting all criteria for inclusion in the study, subsequent dates will be set for the participant to complete all study-related procedures. Visit 2/ Initial MRI Scan: Subjects will complete 60 minutes of structural MRI and resting-state fMRI scans. Structural and functional scans will be obtained in each session on a clinically-approved 3 Tesla Siemens Prisma (Erlangen, Germany) scanner, equipped with 40mT/m gradients and 200 mT/m/s slew-rates, using a Siemens 64-channel head coil. The total time in the scanner will be approximately 60 minutes. Based on our experience, this is well within patients ability to tolerate the scanning procedures without discomfort and without excessive motion. All MRI imaging protocols will be reviewed and approved by CAMRIS. An experienced technician and a member of the study team will be present during the MR session to ensure participant safety and well-being. If the participant complains of feeling claustrophobic and does not wish to complete the MRI, the study will be terminated. Emergency personnel and equipment are immediately available to the MRI room should the need arise. It is possible that during the course of the research study, the research staff may notice unexpected findings on an MRI scan. Should this occur, the findings will be assessed by a trained radiologist. The study doctor will inform research subjects of any significant findings. Visit 3/ TMS + MRI Baseline Scan: Participants will return for a subsequent MRI scan with concurrent TMS brain stimulations. The purpose of this TMS/MRI scan is to probe brain networks prior to the main stimulation protocols, which will occur at the subsequent visits. Brain data from the Initial MRI scan (stimulation target in individualized brain space) will be calibrated with the skin and scalp using a Polaris Vicra camera (Brainsight neuronavigation) to allow marking of the stimulation sites. Our MRI-compatible TMS system (MagPro X100 Stimulator, MRI-B91 TMS coil) is housed in Stellar Chance at the 3-Tesla MRI machine. The apparatus was installed under the supervision of [name]. a member of CAMRIS, and we have attached a signed letter of support from [name] for this protocol. Additionally, participants will complete a series of baseline clinical and neuropsychological assessments. Visit 4-6/ Mini TMS Sessions: Participants will return for 3 consecutive days (+/- 1 day). During each session, subjects will receive theta-burst stimulation (see Huang et al., 2005), which is a slight modification of the FDA-approved protocol for TMS. A normal, FDA-approved clinical application of TMS involves long trains of repetitive TMS applied for approximately 40 minutes, 5 days/week, over 2-6 weeks, for a total of 10-30 TMS visits. We have attached several examples of prior studies which have safely utilized TMS outside of its FDA-approved protocol, even in heightened doses. Our study uses many fewer stimulations than these studies, and we are using the FDA-approved devices for treatment of depression in this protocol (MagPro X100 Stimulator, Cool-Coil B65 TMS coil). Please see the "Background" for more details. Patients will additionally complete a few brief assessments at these visits. Visit 7/ TMS + MRI Scan #2: This visit will mirror Visit 3, the baseline visit. There will be a 2-hour MRI/TMS scan and subjects will complete the same set of clinical and neuropsychological assessments from Visit 3.

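### Stopping medication is a condition of entry to a no-benefit study, but its timing against consent is unclear, its risk is unlisted, and no safety check or action is tied to it

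*Combined protocol and SAP*

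**What the plan says.** All references are to the combined protocol and SAP.

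- **Entry rule.** Under Key exclusion criteria, item 6 excludes "Current use of psychiatric medication, and unable/ unwilling to safely withdraw 2 weeks prior to study". Item 4 covers olanzapine, chlorpromazine and lithium and excludes people who are "unwilling or unable medically to safely withdraw, at least two weeks prior to TMS, from these medications". Target population describes patients with current major depressive disorder, and a subset with persistent depressive disorder.
- **Benefit.** Potential Study Benefits says participants gain nothing directly. Background says the stimulation is not intended as treatment.
- **Visit 1.** Procedures states: "Informed consent will be obtained upon arrival for an initial visit and before any study-related procedures are conducted". It continues: "The rest of this screening visit will include a structured diagnostic interview (SCID-5), psychiatric and medical evaluation".
- **Later visits.** Visit 2 is the MRI used to set the TMS target, and no assessment is listed for it. Visit 3 has clinical and neuropsychological assessments, Visits 4 to 6 have brief assessments, and Visit 7 repeats the Visit 3 set. No instrument is named. The Analysis Plan uses symptom scales, including their slope over rounds of stimulation, as outcomes.
- **Schedule.** Study duration says: "Each subject will complete 8 study visits over the course of ~3 weeks". Seven visits are described; the eighth is not.
- **Risks.** Potential Study Risks covers confidentiality, interviews, MRI and TMS. Risk / Benefit Assessment puts the risk of harm close to nil and names MRI, TMS and symptom assessment as the procedures considered.
- **Suicidality.** The only mention is a form question that begins "Does this research qualify as a clinical investigation that will utilize a test article (ie- drug or biological". It is answered No.

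**The concern.** Coming off medication in order to qualify is a risk that the entry rule itself creates. It falls on people who are depressed at the time and who get no treatment from the study in its place. Three things would normally contain such a risk: consent and a psychiatric evaluation before the drug is stopped, someone checking on the patient while it is stopped, and a statement of the risk. The protocol does not secure the first, does not schedule the second, and omits the third from its risk sections. The minimal-risk conclusion in Risk / Benefit Assessment therefore rests on a list that leaves this risk out.

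**Working it through.** The plan gives no figure to reproduce. The check is to read the sections against each other and see what the visit schedule implies.

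**1. When does withdrawal happen?** Item 4 counts from TMS and item 6 from the study. The three drugs in item 4 are psychiatric medication, so both clocks apply to them.

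- *Reading A: the study begins at Visit 1.* Medication stops about 14 days before consent. The Visit 1 evaluation then follows washout and acts as a check, but only after the drug has been stopped without consent or any study evaluation.
- *Reading B: withdrawal follows Visit 1 and ends two weeks before Visit 3.* The rule that consent precedes any study-related procedure favours this reading. Consent and evaluation come first, but no mood check is listed until Visit 3.

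The Visit 1 demonstration of TMS does not settle the matter, because the text does not say whether the participant receives pulses.

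**2. How long are the intervals?** Inputs: 14 days of washout (Key exclusion criteria) and about 3 weeks, taken as 21 days (Study duration). Assumption: Visits 3 to 7 span *k* days. Procedures fixes only Visits 4 to 6, as consecutive days give or take one. Five successive days gives *k* = 4.

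| Quantity | Formula | *k* = 4 |
|---|---|---|
| B: shortest gap, Visit 1 to Visit 3 | 14 | 14 days |
| B: longest gap within 21 days | 21 − *k* | 17 days |
| B: shortest time off medication through Visit 7 | 14 + *k* | 18 days (2.6 weeks) |
| B: room for a taper within 21 days | 21 − 14 − *k* | 3 days |
| A: time off medication through Visit 7 | 14 + 21 | 35 days (5.0 weeks) |

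The 14-day minimum under B does not depend on *k*. The 17, 18 and 3 do: at *k* = 7 the longest gap falls to 21 − 7 = 14 days, the shortest time off rises to 14 + 7 = 21 days, and no room for a taper remains.

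**3. What is checked, and when?** Of the seven visits described, one (Visit 1) has a stated psychiatric evaluation, one (Visit 2) lists no assessment, and five (Visits 3 to 7) have unnamed assessments. The symptom scales have only an outcome use in the Analysis Plan. No section gives a suicidality measure, a threshold for worsening, a referral step or a rule for restarting medication.

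**4. How many people?** Not stated. Accrual says "we estimate that we will need to consent/enroll up to 95 participants overall", of whom 40 are to complete with usable data and about 55 are not. The share taking medication is not given. Under B, those who fail at Visit 1 would never begin to withdraw, so 95 is a ceiling and not an estimate.

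**The case against.** The plan has real safeguards. Withdrawal must be safe. Item 12 lets the investigator exclude anyone on safety grounds. A study-team member attends the MRI session for the participant's well-being. Resources necessary for human research protection says: "TMS protocols, as well as clinical and neurological assessments, will be administered by specially-trained staff". Data and Safety Monitoring gives the principal investigator a duty to identify adverse events, sets reporting times for serious ones, and stops the study if a serious event raises participants' risk. The Consent Process section has participants reminded that taking part is optional. These all stand, but none names a supervisor, a check or an action for withdrawal.

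Four stronger readings are tempting, and the documents do not support them:

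- *That mood goes unmeasured after Visit 1.* It does not: clinical and brief assessments are scheduled at Visits 3 to 7, and symptom scales are analysed over time. What is missing is any stated safety use, any named suicidality measure, and any check scheduled during washout under reading B.
- *That everyone who withdraws spends two weeks without a mood check.* This follows only under reading B. Under reading A the problem is withdrawal before consent.
- *That participants are not told of the risk.* The consent form is not in the text reviewed and may cover it. The omission is shown only for the protocol's own risk sections.
- *That the No to the suicidality question is an error.* The question concerns drug or biological test articles. The answer simply triggers no check.

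It is also fair to say that a sponsor could stop at clarifying the timing and stating the risk. The follow-up check goes further, but it answers a gap that reading B leaves open and uses staff already in place.

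**Conclusion.** The concern holds and should be fixed, with medium confidence. Withdrawal is an entry condition for currently depressed medication users in a study without direct benefit. Its timing relative to consent and evaluation is not settled. The protocol's risk sections omit it, and no safety check or action is tied to it. Each reading of item 6 leaves a defect: about 14 days off medication before consent, or at least 14 days from the Visit 1 evaluation to the next listed assessment. The longer day counts depend on visit spacing that the documents do not fix and should be taken as illustrations. The number of people affected cannot be derived. The general adverse-event duties do not fill the gap, and a complete consent form would not correct the eligibility, procedures and risk text.

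**What to change.** 1. **Key exclusion criteria, items 4 and 6.** Reword so that withdrawal starts only after consent and the Visit 1 evaluation, with the prescriber's agreement, and is complete at least 2 weeks before the Visit 2 targeting scan. Counting to Visit 3 instead would allow the target to be set on medication or mid-washout while all later scans are unmedicated. If the Visit 1 demonstration delivers pulses to the participant, defer it for anyone still taking an item 4 drug.
2. **Procedures, only for those who withdraw.** Existing study staff make a brief mood and suicidality check during washout, by phone for example, and review the planned symptom scales the same day at Visits 3 to 7. Worsening leads to referral or restart of medication, at thresholds the sponsor sets. If the scales have no suicidality item, add one for this group.
3. **Potential Study Risks and Risk / Benefit Assessment.** Add withdrawal and relapse, and check that the consent form matches. The answer to the suicidality form question can stay.

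**Cost.** A protocol amendment is needed, and a consent amendment only if the form is silent. Each check should take a few minutes of staff time (an estimate; the documents give none). Some participants may be referred out and lost as completers.

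The schedule will lengthen for anyone who needs a taper. With a taper of *T* days starting at Visit 1, a gap of *g* days from Visit 2 to Visit 3, and *k* = 4, Visit 7 falls on day *T* + 14 + *g* + 4. Within 21 days this leaves at most 3 − *g* days for a taper. An assumed 14-day taper puts Visit 7 at day 32 + *g* (about 4.6 weeks plus *g*), and an assumed 28-day taper at day 46 + *g* (about 6.6 weeks plus *g*). Study duration should allow for this.

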
The following documents are currently attached to this item:

There are no documents attached for this item.

Deception

Does your project use deception?

No

International Research

Are you conducting research outside of the United States?

No

Analysis Plan

Clinical outcome will be evaluated on symptom scales in a TMS target x Time ANOVA. Similarly, rate of change (slope) x TMS Target will indicate how rapidly each round of stimulation influences symptoms.

The following documents are currently attached to this item:

There are no documents attached for this item.

Data confidentiality

- Paper-based records will be kept in a secure location and only be accessible to personnel involved in the study.**
- Computer-based files will only be made available to personnel involved in the study through the use of access privileges and passwords.**
Prior to access to any study-related information, personnel will be required to sign statements agreeing to protect the security and confidentiality of identifiable information.
- Wherever feasible, identifiers will be removed from study-related information.**
A Certificate of Confidentiality will be obtained, because the research could place the subject at risk of criminal or civil liability or cause damage to the subject's financial standing, employability, or liability.
- A waiver of documentation of consent is being requested, because the only link between the subject and the study would be the consent document and the primary risk is a breach of confidentiality. (This is not an option for FDA-regulated research.)**
- Precautions are in place to ensure the data is secure by using passwords and encryption, because the research involves web-based surveys.**
Audio and/or video recordings will be transcribed and then destroyed to eliminate audible identification of subjects.

Subject Confidentiality

Patients entering the study will be given a unique identifying code. This code will be used on all data obtained from scans or the medical record. Everything will be immediately coded and this coded information will be stored in secure cabinets inside locked rooms or in password protected, IRB compliant online databases, such as REDCap. Any documents connecting the code with the participant name will also be stored in secure cabinets inside locked rooms or in password protected, IRB compliant online databases, such as REDCap.

Sensitive Research Information*

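### Symptom change is read as the effect of stimulation although there is no comparison group, and the visit schedule does not secure a symptom score just before the first theta-burst session

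*Combined protocol and SAP*

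**What the plan says.** The Analysis Plan is two sentences long, and both concern symptoms. The first reads "Clinical outcome will be evaluated on symptom scales in a TMS target x Time ANOVA". The second adds a slope-by-target term and interprets it as the speed at which each round of stimulation acts on symptoms. Neither sentence names a scale, the baseline, the levels of Time or the levels of target.

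Under Design, all subjects receive active TMS by the fMRI-guided method over three days, "preceded and followed by a 2hr MRI scan during which TMS is administered throughout". No sham, untreated or other comparison group is described there.

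Under Procedures:

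- **Visit 3.** "Participants will return for a subsequent MRI scan with concurrent TMS brain stimulations". Later in the same entry: "Additionally, participants will complete a series of baseline clinical and neuropsychological assessments". The order of scan and assessments is not given.
- **Visits 4-6.** Theta-burst stimulation on three consecutive days, with a tolerance of one day. "Patients will additionally complete a few brief assessments at these visits". Their content, and whether they come before or after that day's stimulation, is not given.
- **Visit 7.** Described as mirroring Visit 3: "There will be a 2-hour MRI/TMS scan and subjects will complete the same set of clinical and neuropsychological assessments from Visit 3". Again no order is given.

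The only bound on the time from Visit 3 to Visit 4 is under Study duration: "Each subject will complete 8 study visits over the course of ~3 weeks". That section then lists seven visits.

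**The concern.** With one actively stimulated group, a change in symptom score between two visits contains everything that happened between them: the natural course of the episode, the effect of answering the same scales repeatedly, any effect of the Visit 3 scan (itself a TMS exposure) and any effect of theta-burst. The Analysis Plan's reading of the slope assigns all of this to stimulation.

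The schedule can widen the problem. If the last full symptom assessment before theta-burst is the one at Visit 3, the change interval includes a gap of unstated length in which no theta-burst is given, and possibly the scan as well. If the Visit 4 assessment is taken after stimulation, or contains no symptom scale, no score marks the point at which theta-burst starts. Neither the order nor the timing can be recovered once data are collected.

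At stake is what the study may say about symptoms. A significant fall could be reported as an effect of theta-burst when the design cannot show that.

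**Working it through.** The documents give no alpha, power, effect size or SD for symptoms, so there is no planned figure to reproduce. Two illustrations show the size of the problem.

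**1. How long can the Visit 3-4 gap be?**

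Input from the documents: about 3 weeks in total, taken as 21 days. Assumptions: Visits 1, 2, 3 on days 0, 1, 2; Visits 4, 5, 6, 7 on days 18, 19, 20, 21.

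- Longest gap = 18 - 2 = 16 days. Shortest, if Visit 4 follows the next day, = 1 day.
- Visit 3 to Visit 7 = gap + 2 (Visit 4 to 6) + 1 (Visit 6 to 7) = gap + 3, so 4 to 19 days.
- Share of the interval before the first theta-burst session = gap / (gap + 3):
  - gap 1 day: 1/4 = 25%
  - gap 7 days: 7/10 = 70%
  - gap 16 days: 16/19 = 84%

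**2. How often would drift alone give a significant time effect?**

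Input from the documents: n = 40 subjects with usable data (Accrual). Assumptions: paired comparison of Visit 3 with Visit 7, two-sided 5%, no theta-burst effect, and mean drift d over the whole interval in units of the SD of change.

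The test statistic is noncentral t with 39 degrees of freedom and noncentrality d × √40. The critical value is 2.023.

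| d | d × √40 | Significant |
|---|---|---|
| 0 | 0 | 5% |
| 0.1 | 0.632 | 9.5% |
| 0.2 | 1.265 | 23.5% |
| 0.3 | 1.897 | 46% |
| 0.5 | 3.162 | 87% |

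**3. How much of this does a Visit 4 baseline remove?**

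Further assumptions: linear drift and the same SD of change. With a 1-day gap, 3 of the 4 days remain after Visit 4, so d becomes 0.75d:

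| d over Visit 3-7 | 0.75d | Significant from Visit 4 |
|---|---|---|
| 0.1 | 0.075 | 7.5% |
| 0.2 | 0.15 | 15% |
| 0.3 | 0.225 | 28% |
| 0.5 | 0.375 | 64% |

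With a 7-day gap, 3 of the 10 days remain, so d = 0.5 becomes 0.3 × 0.5 = 0.15, and the rate falls from 87% to 15%. A later baseline therefore helps more the longer the gap, but in no case does it turn an uncontrolled change into a controlled one.

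**The case against.** The strongest reply has five parts.

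**The plan names interactions, not the Time effect.** Drift common to all targets cancels in a target-by-time interaction. That would be an answer if there were target groups. Background mentions alternative prefrontal sites, but Design gives every subject the fMRI-guided target and the documents describe no allocation to another. What can clearly be estimated is change over time in one group.

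**Scan effects are not shown to be counted as theta-burst effect.** A reader might infer that the baseline is taken after the scan, because the assessments are mentioned last in the Visit 3 entry. The text sets no order, and Visit 7 is said to mirror Visit 3. If the order is the same at both visits, an acute scan effect is in both scores or in neither, and tends to cancel. Contamination by the scan is possible but not established. Nor do the documents say that Visit 3 is the reference level for the ANOVA or the slope.

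**The percentages do not measure baseline placement.** This stands. They arise in any uncontrolled before-after comparison, the drift sizes are assumed, and the Visit 4 figures show that much of the problem can remain.

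**Regression to the mean is uncertain.** This stands too. Entry is by diagnosis with no symptom-score threshold, eligibility is settled from Visit 1, and a subset has persistent depressive disorder. The direction and size of any drift are unknown.

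**Symptoms are not a named outcome.** The primary and secondary outcomes are functional brain activity, and Background says that this is not a treatment study. That lowers the weight. It does not remove the point, because the symptom analysis is the only one that the Analysis Plan specifies.

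**Conclusion.** The concern holds in a limited form. The Analysis Plan's reading of symptom slope as the influence of stimulation is not supported by a design in which everyone receives active TMS to the same kind of target and no comparison is defined. The open order of assessments at Visits 3 and 7, the unstated Visit 3-4 gap and the unplaced assessments at Visits 4-6 can make this worse, because no symptom score need fall just before the first theta-burst session.

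The false-attribution rates of 9.5% to 87% rest on assumed drift of 0.1 to 0.5 SD of change, n = 40 and a two-sided 5% test. They show what the lack of a control can do, and do not estimate what will happen in this study. The gap of 1 to about 16 days rests on an assumed 21-day calendar.

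A reader might also take the period from Visit 1 to Visit 4 as a clean unstimulated control for Visits 4-7. It is not: it contains the Visit 3 TMS scan, and drift need not be linear across the two periods. The change is worth making before more data are collected, but it concerns the symptom analysis and leaves the imaging outcomes untouched.

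**What to change.** 1. State that the clinical assessments are done before the scan at both Visit 3 and Visit 7.
2. Name one brief symptom scale. Give it before stimulation at each of Visits 4-6 and again at Visit 7, and use the pre-stimulation Visit 4 score as the baseline for theta-burst change.
3. State a window for the Visit 3-4 interval and record the actual interval for each subject. Reconcile the visit count (eight stated, seven listed) first, so that the window refers to a settled schedule.
4. In the Analysis Plan, define the levels of Time and of target, or drop the target term if there is only one. Reword the interpretation so that symptom change and slope are reported as uncontrolled change over time and stimulation together.
5. If a comparison of the lead-in slope with the stimulation-period slope is wanted, label it exploratory and give the two limitations stated above.

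The cost is mainly reordering and specifying assessments that are already planned. The downsides are a shorter change interval and a weaker symptom claim.
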